Study design: We propose a blinded control study of real and sham rTMS with a goal of enrolling about eight subjects (age range 21–80 years) in each treatment arm and ten healthy control subjects for normative physiological data (total 26 16). Subjects diagnosed with blepharospasm or cranio-cervical dystonia who receive BoNT therapy at our center will be approached. The BoNT clinic at our center follows more than 250 subjects with dystonia. Subjects followed at our center regularly fill out a self-reported form to document if they have responded to BoNT and the duration of benefits perceived with BoNT therapy. We will enroll only those subjects who report experiencing positive benefits with BoNT but lasting about 10 weeks or less. We will exclude subjects if they report 1) pregnancy; 2) active seizure disorder; 3) significant cognitive impairment; 4) exposure to neuroleptics; and 5) presence of a metallic body such as pacemaker, implants, prosthesis, artificial limb or joint, shunt, metal rods and hearing aid. We will enroll about 10 healthy age and sex-matched subjects controls for normative electrophysiological data. Controls will be recruited through fliers placed across the campus. All controls will be examined by [name] to ensure that they are neurologically healthy.

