Real stimulation: rTMS will be delivered over each anterior cingulate cortex, using a figure-of-eight coil connected to a Magstim machine (Magstim Company, Dyfed, UK). We will apply rTMS with 0.2 Hz frequency to the ACC. We will deliver 180 stimuli (around 15 min) with a stimulator output of 100% active motor threshold (AMT). AMT will be assessed at the tibialis anterior muscle with the figure-of-eight coil. The AMT will be defined as the lowest stimulation intensity required to evoke a 150 μV potential in the target muscle. To determine the stimulation site for ACC, the figure-of-eight/double cone coil will be placed over Fz and then moved over the midline of the brain in 0.5-cm steps anteriorly, until the point of maximum motor evoked potential in the orbicularis oculi (OO) muscle (with a latency of 6–8 msec) is reached (about 3.5 cm medial and 5.5 cm anterior to motor cortex). The coil position will be marked on the skin. Constant coil position will be continuously monitored during the experiment. These rTMS sessions will be repeated on a daily basis over 10 days. During rTMS, all patients will wear ear plugs in order to protect the ears from the acoustic artefact associated with the discharge of the stimulation coil.

Sham Stimulation: During sham rTMS, subjects will undergo the same procedure for identifying stimulus location as used in patients receiving real rTMS. Sham rTMS will be administered using the same Magstim coil as used in real stimulation. This coil will be placed on the patient's head in an identical manner however will not be connected to the Magstim device. Instead another coil will be connected to provide stimulation sound. In each stimulation condition, the Magstim will be placed behind the patient and not visible to him or her. Placebo sham coil which produces discharge noise and vibration similar to a real coil without stimulating the cerebral cortex. During rTMS, all patients will continue to wear ear plugs as instructed during the real stimulation sessions.

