Safety of rTMS: Repetitive TMS can have undesired side effects. Guidelines for the safe use of rTMS were formulated at the 1st International Workshop on the Safety of TMS.²⁴ These were adopted by the International Federation for Clinical Neurophysiology and subsequently updated.²⁵ The proposed study will use TMS parameters well within the published safety guidelines. We will conduct careful monitoring of the participants and follow all recommended precautions for the application of TMS. Subjects will have a urine pregnancy test done on the first day of the scheduled rTMS visit before rTMS is done.

There will be a potential for direct benefit if the study stimulation helps subject's blepharospasm symptoms. Risks include a neck ache or headache. The study procedure may also cause the nearby scalp muscles to twitch. Although TMS has been used for over 20 years, there is a possibility of unknown risks due to TMS.

Data Safety Monitoring Plan

The principal investigator monitors the patient safety and data collection of each study visit. If she feels there is possible harm to subject safety or the possibility of, any harm due to something new that was learned during the study, she will convene a multi-disciplinary committee of at least 2 health professionals to perform a thorough review of the study details.

Patient Stipends

Payments for mileage reimbursement will be paid to study subjects with blepharospasm. If a hotel visit is required, the study team will make the hotel arrangements for the subjects and the cost will be pre-paid.

Control subjects will be paid a flat rate of \$20 or can be paid for mileage, whichever is greater. If you are paid more than \$75, we will need to collect your social security number.

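### The sham procedure is described in two ways that do not agree, and the more detailed one gives no sensation from the coil on the head, which puts the patient blind at risk

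*Combined protocol and SAP*

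**What the plan says.** The Study design paragraph under Methods states the intent: "We propose a blinded control study of real and sham rTMS". How this is done for the patient is set out only under rTMS therapy, Sham Stimulation.

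- **Site-finding.** "During sham rTMS, subjects will undergo the same procedure for identifying stimulus location as used in patients receiving real rTMS". The Real stimulation paragraph defines that procedure as moving the coil forward along the midline until the motor evoked potential in orbicularis oculi is largest.
- **First description of the sham.** "Sham rTMS will be administered using the same Magstim coil as used in real stimulation". Then: "This coil will be placed on the patient's head in an identical manner however will not be connected to the Magstim device". Then: "Instead another coil will be connected to provide stimulation sound".
- **Second description.** After a sentence on keeping the machine out of sight, a fragment without a main verb reads: "Placebo sham coil which produces discharge noise and vibration similar to a real coil without stimulating the cerebral cortex".
- **Other measures for the patient.** The machine stands behind the patient in both conditions, and ear plugs are worn in both.

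Under Safety of rTMS the protocol says of the sensory effects: "The study procedure may also cause the nearby scalp muscles to twitch". The Methods text before Outcome measures has outcome assessors stay away from the TMS sessions, and the videos go to a blinded rater. No section plans a check on whether patients stayed blind.

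**The concern.** Real versus sham is the treatment contrast in the statistical section, so the sham has to be one defined procedure. As written, two operators could follow the same paragraph and deliver different control conditions, one with sound only and one with sound and vibration. The sound-only version is the one described step by step, and it is the weaker for blinding. The coil resting on the scalp does nothing, while the patient has met real pulses during site-finding.

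If patients recognise their arm, part of a real-minus-sham difference in self-rated outcomes may be expectation. The trial would have no means of seeing this, because no question about perceived allocation is planned. A weak sham cannot be repaired once the sessions have been delivered.

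**Working it through.** **1. The two descriptions side by side**

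| Feature | First description | Second description |
|---|---|---|
| Device | Real coil on the head, plus another coil | Placebo sham coil |
| Power to the coil on the head | None | Not stated, but the device makes noise and vibrates |
| Sound | From the other coil | From the placebo coil |
| Vibration | None possible from the coil on the head | Similar to a real coil |
| Muscle twitch | None | Not claimed |
| Position of the sound source | Not stated | Not stated |

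The rows on power and vibration cannot both hold for the coil on the head.

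**2. Can one reading join them?** Suppose the other coil is the placebo coil. The sound is then explained. The vibration is not, because the item on the scalp is still the unconnected real coil and the other coil's only stated purpose is sound.

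**3. What a sham patient has to compare with.** Site-finding relies on evoked motor responses, so it needs delivered pulses, and sham patients have "subjects will undergo the same procedure for identifying stimulus location as used in patients receiving real rTMS". The treatment course follows: 180 pulses at 0.2 Hz is 180 / 0.2 = 900 s = 15 min per session, matching the stated duration, repeated daily over 10 days. Under the first description none of that produces a sensation from the coil on the head. Ear plugs and a hidden machine deal with sound and sight, not touch.

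**4. Exposure by outcome**

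- *CDQ-24 and 7-point rating:* reported by the patient, so directly exposed. The 7-point rating is taken before and after stimulation.
- *Blink rate, sustained blinks, eye-closure time:* scored from video by a blinded rater. Rater bias is dealt with. What remains is an indirect path, through the effect of expectation on the patient's own blinking.
- *Blink reflex recovery:* an electrically evoked EMG ratio, least exposed.

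**5. The plan's own figure.** Inputs from the sample size section: difference 30, SD 20, two-sided alpha 0.05, power 80%. The normal approximation gives 7 per arm. A two-sample t-test with 8 per arm has 79.7% power. The stated 8 per arm is reproduced, and this point does not alter it.

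**6. Size, as illustration only.** The documents give no blinding data. Let p be the proportion in each arm who guess correctly and d the effect of believing one had real stimulation. Both are assumed. Then bias = (2p − 1) × d.

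| | d = 10 points | d = 15 points |
|---|---|---|
| p = 0.7 | 4 | 6 |
| p = 0.8 | 6 | 9 |
| p = 0.9 | 8 | 12 |

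For an outcome with SD 20, 8 per arm and no true effect, a bias of 4, 8 or 12 points would raise the 5% false-positive rate of a two-sample t-test to 6.6%, 11.6% or 20.1%. The SD of 20 belongs to the primary outcome. The documents give no SD for the patient ratings, where the exposure is direct. The table shows how such a bias would act and is not an estimate for this trial.

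**The case against.** The strongest reply is that this is loose drafting of a single two-coil set-up. The fragment comes shortly after the sentence on the other coil and may describe it. That is a fair reading of the grammar, but step 2 shows that it still leaves an inert coil on the scalp.

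Several further objections stand and limit the point:

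- A reader might infer that sham patients hear the click from somewhere else. The position of the second coil is not given, so the documents do not support this.
- A reader might infer that real stimulation will be felt and that patients will therefore know their arm. The safety text says only that twitch may occur. No frequency is given at the treatment intensity, and the intensity of the site-finding pulses is not stated. Each patient is randomised to real or sham, so nobody compares the two kinds of session. Loss of the blind is a risk, not a demonstrated fact.
- A reader might set the illustrative bias against the planned 30-point difference. That difference belongs to the video-scored primary outcome, and nothing in the documents supports a belief effect of 10 to 15 points on it.
- T2 and T3 fall about two and four weeks after the course ends (start at about week 6, two weeks long, assessments at about weeks 10 and 12). Expectation may have faded by then. This does not help the 7-point rating, which is taken around stimulation.
- This is a pilot in 16 patients. A guess question would be imprecise (11 of 16 correct has an exact 95% interval of 41% to 89%), and a late guess can reflect perceived benefit rather than a broken blind.

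**Conclusion.** The sham text is internally inconsistent and should be reconciled. That rests on the wording alone. If the step-by-step version is followed, the patient blind is weaker than it would be with the noise-and-vibration coil already named. This second conclusion assumes that an unconnected coil gives no vibration and that site-finding uses delivered pulses. Both follow from the text.

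The documents do not show that patients will identify their arm, and they do not allow the size of any bias to be derived. The consequence is direct for the patient ratings, indirect for the primary outcome and least for blink reflex recovery. Even with the vibrating coil some risk remains, because the text claims noise and vibration but not twitch. This is a should-fix point.

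**What to change.** Reconcile the Sham Stimulation paragraph to one procedure:

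1. Delete the text on the unconnected real coil and the separate sound coil.
2. State that every sham session uses the placebo coil that produces noise and vibration, held on the head at the same marked position as in the real arm and matched to the real coil in appearance.
3. State which sensations it mimics (noise, vibration) and which it does not (muscle twitch, if that is so).

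Optionally, ask each patient which arm they think they are in and how certain they are. This is best done early in the course, before any benefit can drive the answer. Report the answers by arm, descriptively, and note that 16 patients give a wide interval.

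The cost is a short wording change and, if adopted, one brief question per patient. The placebo coil must be available for all sham sessions. It may not reproduce muscle twitch, so the change reduces the risk without removing it.

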The fundamental mechanism of action for rTMS is modulation of brain excitability. 15 rTMS at frequencies of 5-Hz and higher has been found to transiently enhance the excitability, 16 whereas rTMS at frequencies of 1-Hz and lower has been found to depress the cortical excitability. 17 Many rTMS studies have also shown that repeated sessions of rTMS therapy results in cumulative persistent benefits that can last several weeks. For example, in a recent double blind randomized controlled study, low frequency rTMS delivered over eight weeks to Parkinson's disease patients showed positive clinical benefits that lasted 12 weeks beyond the last rTMS session. 18 In this proposal we plan to employ a two week course of rTMS therapy to achieve sustained benefits. With standard BoNT treatment, the peak-dose benefits are seen at about 4-6 weeks after the administration of injections. We plan to introduce rTMS during this peak-dose period (about 6 weeks after BoNT or T1). We will examine the effects of combined therapy at about 10 weeks after BoNT injections (T2) and at about 12 weeks after BoNT injections (T3). We will also measure the physiological effects at these time points. We will use the blink reflex recovery (BRR) curve that reflects the brain stem excitability. An increased BRR indicates that there is increased excitability of facial motor neurons and bulbar interneurons. BRR has been shown to be increased in a significant proportion of patients with BEB. 19,20 According to the animal model of blepharospasm, one of the underlying mechanisms for increased BRR is that a loss of dopamine-containing neurons in the substantia nigra pars compacta causes a decreased inhibition in the blink circuit.²¹

In summary, BEB is a functionally disabling focal dystonia. BoNT therapy is suboptimal in many BEB patients. rTMS therapy is a promising noninvasive therapy and has shown positive benefits in BEB. rTMS therapy can be Protocol Version 08/10/2015

easily combined with BoNT injections to enhance the effects of BoNT in BEB. We plan to collect pilot data on this novel approach in this one year application. The specific aims for the proposal are:

[figure not shown]
Aim 1: Clinical impact of rTMS therapy in BEB.

[figure not shown]

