We will invite all eligible subjects to an introductory session. During this session the procedures outlined for the study will be explained in detail. We will then obtain an IRB approved informed consent. We will perform medical history and neurological examination using the NINDS Common Data Elements. Each subject will be randomized to receive either real or sham stimulation. We will record the demographics and severity of BEB using the blepharospasm severity scale.²² The BEB subjects followed at our center are scheduled for BoNT treatment about every 12 weeks as per the standard of care. We will start rTMS therapy at about 6 weeks after they have received the BoNT injections. We have chosen this timeframe to coincide the rTMS therapy with the peak-dose effects of the BoNT injections. We will do our best to make sure that the patients are accompanied to the laboratory facility by a friend, relative, or spouse, or we will arrange transportation. Although the physician administering TMS will be aware of the status of the subject in terms of real TMS versus sham-TMS, this physician will play no role in any of the outcome measures, and will not be present during any of the outcome measure assessments. Similarly, the investigators who perform the outcome measures will not be present during any of the TMS sessions, and therefore will remain blinded to the status of the patients with respect to real-TMS versus sham-TMS.

Outcome measures: The primary clinical outcome will be the percentage change in physician rating of BEB symptoms. We will record 5 minute videos of eye blinks for the eye blink rate, number of sustained blinks, and time of eye closure. These videos will be scored by a blinded rater. We will then use the Jankovic rating scale and blepharospasm disability index to rate the improvements. We have IRB approved consent to obtain videos of most patients presenting to our center but the ICF will include a video consent section. The secondary outcome for the study will include the subjective rating by the patients. We will record blink reflex recovery (BRR) as the physiological outcome of rTMS. We will determine the time course effects of rTMS on physiological outcome. We will also determine if the physiological effects correlate with the clinical outcome measures.

Clinical measures:

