Physician rating: We will score the eye blink rate, number of sustained blinks, and time of eye closure. An eye blink will be defined as any visible, bilateral, and synchronous contraction of the orbicularis oculi (OO muscle), causing eyelid drop. Blink rate will be expressed as blinks per minute. Sustained spasms of the OO muscle will not be considered blinks and will be counted separately. The time (seconds) of eye closure whenever blinks cause prolonged eye closure (eyes shut > 2 seconds) will be recorded with a stopwatch.¹⁴

Patient rating: We will administer the Craniocervical Dystonia Questionnaire Description for quality of life assessment. The Craniocervical Dystonia Questionnaire (CDQ-24) is a patient-rated health related quality of life (HR-QoL) measure for craniocervical dystonia. It was developed based on issues that are relevant to patients with BEB. It has been validated for use in clinical research. The CDQ-24 measures the impact of Craniocervical

Dystonia on 5 HR-QoL domains. It is composed of 24 items, forming 5 subscales: stigma, emotional well-being, pain, activities of daily living, and social/ family life. Items are rated on a 5-point scale.²³ Each item consists of five statements representing increasing severity of impairment, scored from 0 to 4. Subjects will be instructed to indicate how they have felt during the past two weeks because of dystonia by selecting one of the five statements for each item. Subjects will also rate their symptoms before and after stimulation using a 7-point nominal scale: 1) excellent, 2) very good, 3) good, 4) average, 5) slightly worse than usual, 6) bad or 7) very bad.

Physiological Measure:

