SAMPLE SIZE, EXPECTED OUTCOME AND STATISTICAL ANALYSIS: With an expected difference of 30% in the primary outcome measure¹⁴ between before (T0) and after rTMS therapy (T1), a standard deviation of 20%, type I error of 5% and power of 80%, the necessary sample size for each group has been determined. In this one year pilot study we propose to enroll a total of 16 BEB subjects with eight subjects in each treatment arm and 16 healthy controls for normative physiological data. Descriptive statistics will be used for the demographic data. Data will be presented as mean (SD) unless otherwise indicated. We will examine each of the dependent measure separately. These include the eye blink rate, number of sustained blinks, the time of eye closure, patient rating of blepharospasm and the BRR cycle. For Aim 1 and Aim2a, each dependent measure will be examined using the following statistical approach. We will conduct a mixed model analysis using time and stimulation arm as repeated factors adjusted for baseline values, and subjects as the random factor. The model will include 2 within-subject factors: treatment (2 levels: active vs sham) and time (3 levels: T1, T1, and T3). If the interaction effects between stimulation arm and time are found as non-significant, they will be dropped. In case of significant main effects, post hoc pairwise comparisons will be corrected using Fisher least significant difference procedure in accordance with the closed test principle; i.e., post hoc comparisons will be declared non-significant if the global p value of the main effect (testing equality of all 2 stimulation arms simultaneously) are non-significant, but will be carried out without further correction in case of a significant global main effect. SPSS version 15.0 for Windows will be used for statistical computations. The 2-tailed significance level will be set at 0.05. For Aim 2b, we will use Spearman correlation test to determine the relation between the change in BRR and change in clinical scores at T2 compared to T1 and at T3 compared to T1.

POTENTIAL PROBLEMS

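### The primary physician rating is three separately tested measures with no lead measure or success rule, so the planned 5% error and 80% power are not secured together

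*Combined protocol and SAP*

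**What the plan says.** All references are to the combined protocol and SAP.

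- **Outcome measures (Methods):** "The primary clinical outcome will be the percentage change in physician rating of BEB symptoms". The same paragraph adds: "We will then use the Jankovic rating scale and blepharospasm disability index to rate the improvements". It makes the patients' own rating secondary and blink reflex recovery (BRR) the physiological outcome.
- **Clinical measures, Physician rating:** "We will score the eye blink rate, number of sustained blinks, and time of eye closure". Sustained spasms are counted apart from blinks.
- **Sample size, expected outcome and statistical analysis:** the planning figures are for a single primary measure: an expected difference of 30%, with "a standard deviation of 20%, type I error of 5% and power of 80" (per cent), and eight patients per arm. Then: "We will examine each of the dependent measure separately". The list that follows has five entries: the three physician-rated variables, patient rating and BRR. It includes neither the Jankovic scale nor the disability index. Also: "The 2-tailed significance level will be set at 0.05".
- **The only multiplicity rule,** in the same section, is Fisher's least significant difference: "post hoc comparisons will be declared non-significant if the global p value of the main effect" is itself non-significant.
- **Background:** "We plan to collect pilot data on this novel approach in this one year application".

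**The concern.** The sample size, the 5% and the 80% all belong to one measure, but the outcome they are meant to serve is three measures, each with its own model and its own 0.05 test. The plan does not say whether the primary is met when one of the three is significant, when all are, or when a particular one is. These rules have different error rates and different power.

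The Fisher gate does not settle this. It asks whether the arm effect for a given measure is significant before pairwise comparisons on that measure are read. It does not link one measure to another.

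Two things are at stake: whether a reader can hold the result to the plan's own 5% and 80%, and which measure a follow-on trial would be built on.

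**Working it through.** **Inputs.** From the sample-size section: difference 30, SD 20, two-sided alpha 0.05, power 0.80, 8 per arm. From the Physician rating paragraph: three measures. Assumed, because the documents give no value: an equal pairwise correlation r among the three, varied from 0 upwards, and normally distributed data. One test is counted per measure.

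**Step 1: reproduce the planned size for one measure.** Reading 30/20 as an active-sham difference, d = 30/20 = 1.5.

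- Normal approximation: n = 2 × [20 × (1.960 + 0.842)/30]² = 6.98, so 7 per arm.
- Two-sample t-test: n = 8.06 for 80% power; power at 8 per arm is 79.7%.

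Eight per arm therefore fits one measure tested once.

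**Step 2: any one of three counts.** If independent, 1 − 0.95³ = 0.143. With correlation, from simulated two-sided t-tests, 8 v 8, no true effect on any measure:

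| r | False-positive risk |
|---|---|
| 0 | 14.4% |
| 0.5 | 12.9% |
| 0.8 | 10.1% |
| 0.9 | 8.4% |
| 0.95 | 7.6% |
| 0.999 | 5.4% |

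The normal-theory version gives 7.3% at r = 0.95, hence about 7.5%. A version closer to the planned model (arm effect on the mean of T2 and T3 adjusted for T1, within-patient correlation 0.5 assumed) gives 14.3%, 12.8%, 10.4% and 9.0% at r = 0, 0.5, 0.8 and 0.9.

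**Step 3: all three must be significant.**

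- *Error.* If no measure has a true effect, 0.0% at r = 0 to about 2% at r = 0.9. If two measures have a true effect of d = 1.5 and the third has none, about 3% (at r = 0: 0.05 × 0.797² = 0.032). It approaches 5% only as the other two effects become large, so it stays below 5%.
- *Power,* with d = 1.5 on every measure and 8 per arm: if independent, 0.797³ = 0.506. Simulated: 50.2%, 59.9%, 67.6% and 71.3% at r = 0, 0.5, 0.8 and 0.9.

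**Step 4: sensitivity to the meaning of 30/20.** The section words the 30% as a change from before to after rTMS. Taken literally, with 20 as the SD of that change, a paired t-test on 8 patients has 95.1% power for one measure. Requiring all three independent measures then gives 0.951³ = 0.860, above 80%. The loss in Step 3 therefore depends on the active-sham reading; the inflation in Step 2 does not. The paired reading would need only 5.7, so 6, patients, whereas 8 matches the two-sample calculation. The planned model also compares arms.

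**The case against.** The strongest reply is that this is a one-year pilot of 16 patients, that examining several measures separately is usual at this stage, and that the sentence about doing so describes modelling and not a rule for claiming success. Much of that stands. It lowers the weight, and it rules out several stronger readings:

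- *A reader might infer that the trial runs a 14% false-positive risk.* The documents do not support that. They nowhere say that one positive measure suffices, and 14% needs independence. The three measures come from the same short video, so a high correlation cannot be excluded; the conditional range runs from just above 5% to 14%. Counts and seconds in 16 patients may also depart from normality.
- *A reader might take 0% to 2% as the error of the all-three rule.* It is so only when all three effects are null.
- *A reader might conclude that power is certainly lost.* Step 4 of the working shows that this depends on how the planning figures are read.
- *A reader might count five tests,* giving 1 − 0.95⁵ = 22.6%. Patient rating and BRR are not part of the primary, and no test is stated for the Jankovic scale or the disability index. The Outcome measures paragraph could even be read as making those scales the rating. That leaves the primary less defined, but does not add tests.

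What the reply does not remove is that the plan itself sets 5% and 80% for a single primary measure and declares significance at 0.05, without saying which measure that is.

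**Conclusion.** The concern holds as a gap in definition: the primary has no lead measure, composite or success rule, so the plan's 5% and 80% are not secured together.

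- **If any one measure counts,** the 5% is exceeded: about 14% at independence, 10% at r = 0.8 and 7.5% at r = 0.95, nearing 5% only when the measures are almost identical.
- **If all three are required,** the error is kept below 5%, but power is about 50% to 71% for r = 0 to 0.9.
- **If one measure is named in advance,** the error is 5% and power is 79.7%.

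The error figures rest on assumed correlations and normal data. The power figures also rest on the active-sham reading of 30/20 and an equal effect on all measures. The change should be made, but its weight is modest because the study is a pilot.

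**What to change.** Before unblinding, name one physician-rated measure as the single primary. Name one deciding active-versus-sham contrast at two-sided 0.05: either the arm effect over the post-rTMS visits or the comparison at one named visit. Label the other measures as secondary, including the Jankovic scale and the disability index if not chosen. Restate the 30% and 20% for the chosen measure, and say whether they describe a difference between arms or a change within patients.

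Splitting alpha across the three measures is a poorer alternative. At 0.05/3 and 8 per arm, power for any given measure falls to 61.7% on the active-sham reading, and 80% would need 11 per arm.

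The cost is wording only, with no new data, visits or patients. Power for the chosen measure is not known from the documents until its planning figures are restated. The downside is that a benefit seen only on another measure becomes a secondary finding.
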